Aim 1: To evaluate the effectiveness of the REAL HEALTH-Diabetes lifestyle change program comparing in-person (IP) group and telephone conference call (TCC) group intervention to individual dietitian referral for MNT.

H1a. Primary outcome. Weight loss: We hypothesize that the IP and TCC lifestyle groups will demonstrate greater weight loss than MNT at 6 months, and that the lifestyle group participants will have more sustained weight loss at 12, 24 and 36 months. The sample size of 210 provides 80% power to detect a 3.5% difference between any two groups adjusting for three group comparisons, 10% drop-out rate, and intraclass correlation (ICC=0.02).

H1b. Secondary outcomes. Medical outcomes: We hypothesize that compared to individual MNT, participants in the IP and TCC group interventions will maintain or improve HbA1c, blood pressure, and lipids from baseline with reduced medication use

(dose and cost) to treat these conditions, both at the end of the intensive intervention and at follow-up.

H1c. Behavioral and psychosocial outcomes: We hypothesize that compared to MNT, the lifestyle groups will have greater improvements from baseline in health behaviors and the patient-reported outcomes of self-efficacy and health-related quality of life.

Aim 2: To evaluate the reach, adoption, implementation fidelity, and maintenance of the two adapted Look AHEAD lifestyle change programs (IP and TCC) at the three community health centers, comparing factors across centers using the RE-AIM Model Dimension items checklist. We will use a mixed methods approach, first using structured interviews with participants who would be eligible to participate to inform the design of the telephonic intervention, then using provider surveys and participant structured interviews in years 2-4 to assess engagement and adoption by providers and compare responders and non-responders. Participant structured interviews will be conducted when the participant has completed the active intervention at year 2. Structured interviews will be administered by non-blinded study staff, and will follow the same procedures as described for the initial structured interviews that indicate the study design [see V. Study Procedures]. We will also collect quantitative indicators of implementation.

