Research Visits 2-5 will last about 2 hours. Participants will be scheduled for a research visit 6, 12, 24, and 36 months after the initiation of the intervention with a \pm 2 month visit window. Any clinical data or questionnaires that may be collected outside of the window will count for the closest visit window, with the date of data collection documented. The visit may coincide with a usual care appointment. They will receive an appointment reminder letter [see “16. RV2 Appointment Reminder Intervention and Usual Care”]. Participants will need to fast from midnight until the morning of the visit and wait until after their blood samples are drawn to take any diabetes medications. The participants will be met by a member of the study team at their health center. Participants will be asked to provide a blood sample of 6 cc taken by trained phlebotomist in the health center clinical laboratory. Subject’s blood pressure will be taken resting and will be measured in duplicate using an automated device. Height and weight will be measured and then entered into the electronic medical record to derive BMI values. Once blood samples, blood pressure and height and weight are taken and processed as outlined above, participants may take their diabetes medication(s) and will be provided a nutrition bar. Then they will be asked to complete self-administered study questionnaires on paper or via RedCap as outlined above. Any changes in medication doses for glycemic control, blood pressure and lipid management will be reviewed and confirmed by cross checking in electronic medical record.

Research visits will be conducted by a health center medical assistant, RN, or LPN who has received CITI certification in Human Subjects research and has been trained and will be funded by the REAL HEALTH-Diabetes study for this purpose. Central study personnel will support health center staff in training and assessment. Health center staff will also be supervised by the health center-based clinician co-investigators.

Participant compensation. Study participants will receive payment of \$25 for completing follow up assessments at 6 months and 1 year, \$50 at 2 years, and \$100 at 3 years to promote retention for outcome assessment.

Study outcomes/ data to be collected

AIM 1 Outcomes and Assessment Protocol

Measures at baseline and follow up assessments

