8. Health behavior: Dietary behavior will be assessed using the Fat-Related Diet Questionnaire (20,21) and the Restraint subscale of Dutch Eating Behavior Questionnaire which rates frequency of using ten different restraint behaviors (22). Two questions from the Dietary Screener Questionnaire (DSQ) used in the NHANES 2009-2010 series, will be used to assess intake of sweetened beverages (23). Activity behavior will be assessed by the Paffenbarger Physical Activity Survey and self-reported minutes of physical activity (24).

9. Self-determination theory measures:

a. Autonomy: Treatment Self-Regulation Questionnaire (TSRQ). An 18-item tool that measures reasons for engaging in a particular behavior (e.g., diet) to assess the degree to which the individual holds autonomous reasons for this behavior, i.e., a sense of choice vs. a need to comply will be administered at baseline, 6, 24, and 36 month visits (25). It has been shown to predict better attendance, greater weight loss, greater maintenance of weight loss and better exercise regimen, as well as greater adherence and health behavior change for other behaviors (e.g., smoking, medication) (26-29).

Health Care Climate Questionnaire (HCCQ). A 15-item measure that assesses the degree to which respondents find their clinical and weight loss teams to be supportive of their autonomy vs. controlling will be administered at 6 month and 24 month visits. For example, do providers appear to take the patient’s perspective, minimize control, and foster flexibility and choice, promoting feelings of respondent competence and motivation to change behavior (25).

b. Competence/self-efficacy will be measured using the Diet Self-Efficacy scale, a 16-item scale scored from 1 to 5 that measures confidence in one’s ability to adopt healthy dietary behaviors and the Exercise Self-Efficacy scale, a 5-item scale scored from 1 to 7 that measures confidence

in one's ability to persist with exercise in situations that involve potential barriers, e.g., negative affect and time constraints (30,31).

c. Relatedness. The construct of relatedness from self-determination theory will be measured using the Social Support for Healthy Behaviors scale, a 22-item scale that assesses perceived social support from family and friends that is specific to healthy eating and exercise behaviors, with good test-retest and internal consistency reliabilities and construct validity (32).

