10. Health literacy and numeracy will be measured with the NVS (newest vital sign), a 6-item food-label based assessment validated in English and Spanish, at baseline only (33).

11. Food insecurity will be measured at baseline, 12 months, 24 months and 36 months with the U.S. Household Food Security Survey Module: Six-Item Short Form Economic Research Service, USDA, available in English and Spanish (34).

11. Medication adherence will be measured at baseline, 6 months, 12 months, 24 months, and 36 months using the 8-item Morisky Medication Adherence Scale (35).

12. Satisfaction with care will be measured using survey instruments developed for the IDOLc pilot which were adapted for pertinence from the Diabetes Quality of Life Measure (DQOL) (36) and satisfaction surveys used in previous lifestyle intervention research (37). In addition, participants will be asked questions at the end of the 6-month intervention period and at 2 years at the end of the intervention period to rate their level of satisfaction with the program and their interactions during the visits with the dietitian.

13. Other Diabetes Care and Costs will be assessed at 6 months, 12 months, 18 months, and 24 months to determine the cost-effectiveness of all arms of the study.

Patient-reported outcomes will be completed by participants in a quiet room at the time of outcome assessments either on paper or via RedCap web interface. Every effort will be made to ensure completion at the time of the research visit, but if this is not possible participants may complete assessments later. Outcomes assessors will be trained to review and administer these instruments and to help participants when necessary. Outcomes assessors will be blinded to study arm. Participants will not be eligible for compensation until all elements of a research visit are complete.

These questionnaires typically take about 40-50 minutes to complete.

Table 2. Schedule of questionnaire administration

Questionnaires (S/I)*	RV1 (0 Mos)	RV2 (6 Mos)	RV3 (12 Mos)	18 Mos	RV4 (24 Mos)	RV5 (36 Mos)
Literacy Questionnaire (I)	X					
Demographic information (S)	X					
Medication and Health Service Utilization (I)	X	X	X	X	X	X
Contact Information (S)	X	X	X		X	X
Health History (S)	X				X	X
Weight History (S)	X					
Treatment Self-Regulation Questionnaire (S)	X	X			X	X
Exercise Self-efficacy Scale (S)	X	X	X		X	X
Diet Self-efficacy Scale (S)	X	X	X		X	X

Paffenbarger (S)	X	X	X		X	X
Fat-Related Diet Behavior (S)	X	X	X		X	X

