Program Satisfaction (S)		X			X	
Satisfaction Surveys (S)	X	X	X		X	X
Morisky Medication Adherence (S)	X	X	X		X	X
EQ-5D (S)	X	X	X		X	X
Problem Areas in Diabetes (PAID) Scale (S)	X	X	X		X	X
Restraint Subscale of the Dutch Eating Behavior Questionnaire (S)	X	X	X		X	X
PHQ-8 (S)	X	X	X		X	X
Social Support for Healthy Behaviors (S)	X	X	X		X	X
Food Insecurity (S)	X		X		X	X
Health Care Climate Questionnaire (S)		X			X	X
Dietitian Intake Questionnaire (I)	X					
RV4 Structured Exit Interview (I)					X	
Other Diabetes Related Care and Costs Questionnaire (S)		X	X	X	X	
PCP Questionnaire (S)			X		X	

*(S) Self-administered, (I) Interviewer-administered

X = Questionnaire being administered at visit

Aim 2: Implementation analysis

We have designed and will evaluate the project according to the RE-AIM model. The RE-AIM framework includes participant (Reach, Effectiveness, Maintenance) and organization level (Adoption, Implementation, Maintenance) elements to capture the full effect of not only a program's efficacy but also its broader impact and sustainability.

Variables to be collected to gauge overall efficacy of REAL HEALTH-Diabetes are listed after the corresponding RE-AIM element of interest. This section is modeled after a framework proposed in “RE-AIM for Program Planning” by Belza B. et al. (http://www.prc-han.org/docs/RE-AIM_issue_brief.pdf) (38).

Reach

- What percent of your target population (those who are intended to benefit from your program) will participate in the program?
 - Many patients with diabetes are not ready or able to participate in this program. We estimate a maximal eligibility rate of 20% of the population at a given time. This will be the denominator by which we calculate reach.
- Does your program reach those most in need? Are participants representative of the targeted population?
 - Measure: Participation rate at each center and within R/E groups

Effectiveness—see Aim 1.

- Weight loss
- Medication reduction
- Behavior change
- HRQoL and diabetes-specific quality-of-life
- Cost—see Aim 3
- Participation (attendance)

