Risks of exercise: There is a risk in all exercise of pulling or straining a muscle. Participants will be advised to slow down or stop if they experience any pain and advised to inform their dietitian if they have muscle pain from the exercise at the next appointment. Some participants may feel tired or become short of breath from the exercise. Participants will be advised to stop exercising if they experience any pain or pressure in the chest or have moderate shortness of breath and to call 911 if they feel there is any risk of having a heart attack.

Subject confidentiality will be protected. In order to protect the privacy of the participants, they will be assigned a coded, anonymous numerical identifier at enrollment. Study specific data (mostly from the survey instruments) will be linked to this anonymous coded identifier only, and will not be part of the medical record. Routine diabetes labs and weight, along with medication

changes, will be entered into the electronic medical record by the study MA and provider at each site to promote safety and integration of the intervention with usual care.

For study-specific data, the key will be stored in the Diabetes Research Center in a locked cabinet and in her password-protected hard drive. Only study personnel who have undergone appropriate human research training and signed standard confidentiality agreements will have access to these data. All subject-related documents will be stored in locked file cabinets within locked offices. However, it cannot be guaranteed that a breach will not occur.

VIII. POTENTIAL BENEFITS

a. Potential benefits to participating individuals

Participants will receive usual nutrition and lifestyle care at MGH Nutrition Services or a free group in-person or telephone conference call group based nutrition and lifestyle intervention program. Based on our pilot data it is likely that participants in all arms will lose weight and experience improvements in blood glucose control, blood pressure, and lipid levels and reductions in some medications to treat these conditions.

b. Potential benefits to society

On a societal level, this proposal will be a next step in translating an evidence-based lifestyle intervention into high-value clinical care of type 2 diabetes participants in the community health center setting. Results and materials from this project will be freely available on a study website.

IX. MONITORING AND QUALITY ASSURANCE

a. Independent monitoring of source data

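### Assessor blinding is stated but not protected: assessors review forms likely to reveal the arm, and nobody is named for the medication cross-check

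*Combined protocol and SAP*

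**What the plan says.** The blinding statement is one sentence in Section V, after the list of Aim 1 measures: "Outcomes assessors will be blinded to study arm". No method for keeping the blind is given there or elsewhere. A sentence just before it sets the assessors' duties: "Outcomes assessors will be trained to review and administer these instruments and to help participants when necessary".

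The instruments include a form given at 6 months and 2 years on which participants "rate their level of satisfaction with the program and their interactions during the visits with the dietitian". Table 2 lists Program Satisfaction at RV2 and RV4. They also include the Health Care Climate Questionnaire (HCCQ), which asks how far "respondents find their clinical and weight loss teams to be supportive of their autonomy". The text places it at 6 and 24 months, and Table 2 adds 36 months.

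On medication, Section V.2 (Research Visits) says: "Any changes in medication doses for glycemic control, blood pressure and lipid management will be reviewed and confirmed by cross checking in electronic medical record". It names nobody for this. The same section has visits run by a medical assistant or nurse from the health center. Section VII, in the confidentiality paragraph, says that routine labs, weight and medication changes "will be entered into the electronic medical record by the study MA and provider at each site".

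The plan separates staff in one place. For the Aim 2 participant interviews (Section II), "Structured interviews will be administered by non-blinded study staff".

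**The concern.** The arms are an in-person group, a telephone group and referral to a dietitian. A form rating the program, or one asking about a weight loss team, is likely to tell the person checking it which kind of care the participant received. If that person is the outcome assessor, the plan's own procedures work against the blinding it claims.

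The medication record is a second possible route. In the lifestyle arms a study provider reviews glucose records and adjusts doses (Section IV.c), whereas usual-care participants stay with their primary care physician (Section VII). A change made by the study provider may therefore hint at the arm.

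At stake are the questionnaires that staff help to complete, weight and blood pressure measured by a returning assessor at 12 to 36 months, and a trial report that would describe assessor blinding the procedures do not secure.

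**Working it through.** No arithmetic applies. The plan gives no figure for blinding, and blinding enters none of the sample-size inputs in Section VI.d (difference 3.5%, SD 5.5%, significance level 0.0167, ICC 0.02, 10% drop-out). The check sets the relevant passages side by side.

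1. **Do assessors see the revealing forms?** The duty to review and administer covers the instruments without exception. Table 2 lists Program Satisfaction and the HCCQ with no separate handler. Section V also withholds participant payment until every element of a visit is complete, so someone has to check that these forms were done. As written, that can be the assessor.

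2. **Do the forms reveal the arm?** The forms are not shown, so this is inferred from their descriptions. It is likely for Program Satisfaction and plausible for the HCCQ, but certain for neither.

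3. **Do assessors see medication changes?** The plan does not say. The cross-check in Section V.2 has no named person. The Aim 1 list has medication data captured by chart review and telephone interview, and the Aim 3 text has them collected by telephone every 6 months. Table 2 marks the medication and health-service form as interviewer-administered at every visit without saying who interviews. Section VII has a site study MA and the provider enter weight and medication changes, and Section V.2 allows a health center medical assistant to run visits. Nothing states that these are different people, or that they are the same.

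4. **Are travel and telephone costs a further route?** Section V (Aim 3) collects them at RV2, RV3 and RV4 and names no collector. Table 2 has no row for this form, and the data variables list places it at RV1 and RV5. The timing has to be reconciled before this form can be relied on as evidence.

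5. **Which outcomes are exposed?** Section V.2 places blood draw, blood pressure and weight before the questionnaires.

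| Outcome | Exposed through the forms? |
|---|---|
| Weight and blood pressure at RV2 | No: taken before the RV2 forms |
| HbA1c and lipids, all visits | No: drawn by phlebotomists and run in the clinical laboratory |
| Questionnaires completed with staff help, from RV2 | Yes |
| Weight and blood pressure at RV3 to RV5 | Only if the same assessor returns |

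The order of procedures does not guard against what site staff may have learned from the record before RV2. Whether that happens depends on the staffing left open in step 3.

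**The case against.** The strongest reply is that the text shows a risk and not a failure. Nothing says that assessors do the medication cross-check. Medication changes also do not identify the arm: in the pilot, 38% of the MNT group stopped or reduced diabetes medication, and the blood-pressure provision in Section IX.b, which involves the study provider, is not restricted by arm. Program Satisfaction is self-administered, asks partly about dietitian visits that all arms can have, and can be completed in RedCap away from the clinic. Help is given only when needed. Participants know their own arm, so blinding the assessor cannot remove reporting bias from what they write. No continuity of assessors is stated. Blood pressure is taken in duplicate with an automated device.

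Most of this stands, and it limits the point. A reader might infer that the blind is gone from the 6-month visit on, or that every later outcome is affected. The documents do not support either reading: the form contents are inferred, same-assessor continuity is not stated, and laboratory outcomes do not pass through the assessor's hands.

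What the reply does not answer is the absence of any safeguard. The assessors' duty to review covers a form about the program, next to a sentence saying they are blinded, and the plan's one explicit separation of staff, for the participant interviews, is not extended to that form or to the medication check.

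**Conclusion.** Assessor blinding is claimed without protection and is likely to be compromised after the RV2 questionnaires. This rests on two assumptions: that Program Satisfaction and the HCCQ show what their descriptions suggest, and that the assessor reviews them as Section V says. Carry-over to weight and blood pressure at 12 to 36 months needs a third, that the same assessor returns.

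A reader might also infer that the primary outcome is biased. The documents do not show this: the 6-month weight is measured before the forms are completed, and prior knowledge from the record is only a possibility that the staffing text leaves open.

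The size of any bias cannot be measured from the documents. It would depend on how many participants are helped and on whether that help differs by arm, and neither is given. The model and sample size are unaffected. This is a cheap improvement to conduct and reporting, not a threat to the primary analysis.

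**What to change.** - Send Program Satisfaction and the travel, telephone and cost forms by RedCap link or sealed envelope to the coordinating center, so that the assessor does not review them. By the same reasoning, include the HCCQ. Let the center confirm completeness for participant payment.
- Name who does the medication cross-check, and choose existing study staff who do not measure outcomes. The plan already has central personnel (Section V.2) and non-blinded study staff (Section II, Aim 2).
- Keep weight and blood pressure first at every visit.
- At RV2, record the assessor's guess of arm with a don't-know option and the reason for the guess, because a guess can also reflect visible weight loss.
- Reconcile the visits at which the travel and telephone form is collected: Section V (Aim 3) against the data variables list.
- If these changes are not made, limit the blinding claim to the 6-month weight and blood pressure.

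The cost is some wording on form handling and staff roles, one added field, and slightly more central work per visit. The documents do not say whether current staff have capacity for that work.

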- Another member of the household is a study participant or a study staff member
- Overt hypo- or hyperthyroidism, defined as abnormal free T4, who have had thyroid medication adjustments in the last three months
- Long term use (in the 6 months prior to study entry) of medications likely to cause weight gain or inhibit weight loss (e.g. corticosteroids, with the exception of maximum dose of prednisone 10 mg or equivalent)
- Previous or planned gastric bypass
- History of cancer, other than non-melanoma skin cancer, that required therapy in the 5 years prior to randomization.

Participants must have (1) a medical need and willingness to lose at least 5% of body weight and (2) medical clearance to participate safely in the exercise component of the program which has a goal of increasing moderate intensity activity to at least 175 minutes per week. Each participant will be asked to keep a 1-week food, exercise and blood glucose record prior to meeting with the dietitian for a screening appointment. In order to participate in this study, participants must complete at least 5 of the 7 days of the food, exercise and blood glucose diary. Participants will have an intake interview with a dietitian to evaluate readiness to participate in a lifestyle intervention program. This interview will not determine eligibility but rather foster the ability of each patient to determine his/her own readiness to commit to the program and to help him/her decide whether to enroll or defer enrollment until another time when other competing priorities and identified barriers to successful participation are reduced.

b) Source of participants and recruitment methods

Participants will be primarily recruited from health center primary care practices. Participants also will be recruited from MGH primary care practices, MGH Diabetes Center, Newton-Wellesley Hospital and North Shore Medical Center. Others may participate as long as they have a primary care provider or treating provider who can approve their participation. Participants can be identified by their primary care physician, endocrinologist, nurse, or nurse practitioner. Patient registries will also be used to generate lists of potential participants for providers to review and identify eligible participants. Patient registries will also be used to generate lists of patients who have agreed to be directly contacted for research in a clinical care setting.

From this potential pool, we will recruit using the following steps:

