1) Conduct an electronic chart review using the TopCare or RPDR diabetes list to verify eligibility criteria and PCP linkage. The current population of each health center is described in Table 1.

Table 1. Characteristics of community health center populations

	Racial/ethnic distribution of population			Number with DM	Prevalence of DM	Target n to recruit
	W	H	AA			
Charlestown	79%	9%	5%	1085	10%	~45
Chelsea	28%	56%	9%	2691	19%	~85
Revere	64%	16%	5%	2120	15%	~85

- 2) Obtain permission for initial contact from each potentially eligible patient's primary care or treating physician (PCP) [see "1. PCP Patient Recruitment Email"]. After permission received, study staff will check to see if participant is in the process of being contacted or in the process of enrolling in another study (GRADE) that is recruiting concurrently. If participant has already been contacted and is interested in GRADE, we will not contact.
- 3) Send an introductory letter [see Introductory Patient Letters] to PCP-approved participants and to patients who have agreed to be directly contacted for research describing the study and procedures to opt out of further contact. The introductory letter will be sent along with a brochure. In the brochure, potential subjects will be able to learn more about the study. The brochure will also include a study phone number and a study email address that participants can call or email to either decline further contact or to request that a study coordinator contact them.
- 4) If no answer is received after 7 days have passed, the potential research subject will be contacted by study staff to determine his/her willingness to participate.
- 5) If the subject is willing to participate, he/she will then undergo initial screening [see "3. Screening Phone Call Script"]. During this phone call, the study will be explained in further detail, subject questions will be answered, and an initial screening questionnaire to assess eligibility will be completed. Participants who remain eligible will be scheduled for an initial research visit and/or an introductory orientation session based on preference and mailed a 1-week food, exercise and blood glucose record, an appointment reminder letter, and an informed consent form [see "4. RV1 Appointment Reminder" and "5. Informed Consent Form"] (described below "SUBJECT ENROLLMENT"). We will also send them a link to a video about the study if they have access to email. (See **Figure 1** Recruitment flow).

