Sample size/power calculation.

H1a. IDOLc preliminary data showed 6.7% mean weight loss at 6 months in the lifestyle intervention group, which was 4.1% greater than the MNT group. The standard deviation of percent weight loss in the pilot cohort was 5.5. Our aim is to detect a clinically meaningful 3.5% difference between any of the two study groups (where weight maintenance is defined as weight change <3%⁷¹). We use the conservative Bonferroni method to adjust for 3-arm multiple comparisons, which reduces the two-sided significance level to 0.0167 (0.05/3). Assuming a SD of 5.5%, the study will need an effective sample size of 54 per arm to detect a 3.5% difference with 80% power. We assume a conservative intraclass correlation coefficient of 0.02 within each counseling group, which translates into an inflation factor of 1.2, and 10% drop-out rate based on our prior results and the fact that participants receive primary care at study sites. The final sample size will be 210, 70 per arm.

Further analyses:

H1b. We hypothesize that participants in the group interventions will maintain or improve HbA1c, blood pressure, and LDL with reduced medication use (dose and cost) to treat these conditions, both at the end of the intensive intervention and at follow-up, compared to the MNT arm. Medication reduction is an outcome that is meaningful to participants and reduces costs to payors (40,41). Based on our preliminary data, in which 61% of the lifestyle group had improved HbA1c on less medication compared to 31% in the MNT group, we have 81% power to detect a difference of 33% with an effective sample size of 54 per group, adjusting for the 3-arm comparison. We will perform further analyses employing number of medications, insulin use, insulin doses, and Diabetes Medication System Questionnaire, PAM-D or similar weights to model differences in medication intensity among groups (42,43).

H1c. Using the standard deviation estimates from our previous data (44,45), the study will have 80% power to detect a mean difference of 0.35 (on a scale of 1 to 5) in the change of low-fat diet self-efficacy measure between the two lifestyle change arms or between either lifestyle change and the MNT arm, assuming a standard deviation of 0.55. For the change in exercise self-efficacy measure, the study will have 80% power to detect a mean difference of 0.88 (on a scale of 1 to 7), respectively, assuming a standard deviation of 1.4.

Aim 2:

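### The level of reach in Aim 2 is set by an unsourced 20% eligibility estimate, and the plan does not say who belongs in the numerator

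*Combined protocol and SAP*

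**What the plan says.** Section V (Aim 2: Implementation analysis, Reach) asks what share of the target population will take part. It answers with an assumption, "We estimate a maximal eligibility rate of 20% of the population at a given time", followed by the rule "This will be the denominator by which we calculate reach". No source or derivation is given. A second reach item, on representativeness, is listed as "Measure: Participation rate at each center and within R/E groups", with neither its numerator nor its denominator defined.

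Section II (Aim 2) places the evaluation of the in-person and telephone lifestyle programs "at the three community health centers, comparing factors across centers using the RE-AIM Model Dimension items checklist".

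On enrollment, Section VI.d (H1a) says "The final sample size will be 210, 70 per arm". Section III.b, which describes recruitment from the health centers, adds: "Participants also will be recruited from MGH primary care practices, MGH Diabetes Center, Newton-Wellesley Hospital and North Shore Medical Center". It also admits other people whose own provider approves. The last inclusion criterion in Section III.a and the end of Section III.b likewise open the trial to patients of other practices.

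On eligibility checks, step 1 of the recruitment sequence in Section III.b is to "Conduct an electronic chart review using the TopCare or RPDR diabetes list to verify eligibility criteria and PCP linkage". In step 5, during the phone call, "an initial screening questionnaire to assess eligibility will be completed".

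**The concern.** Reach is a proportion, and the plan fixes its denominator by assumption. The numerator cannot exceed the planned enrollment. In a trial that enrolls fully, the level of reach therefore follows from the 20% and the sample size, and it does not respond to how many patients were in fact eligible. Meanwhile, staff check eligibility patient by patient, and nothing in the plan links those checks to the reach calculation.

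The numerator is also open in two ways. Aim 2 speaks of the two lifestyle programs, but the plan does not say whether participants randomized to dietitian referral count as reached. Nor does it say whether recruits from outside the three centers count, although they do not belong to the three-center population.

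Determining reach is part of the project's stated goal (rationale, Section I.c), and greater reach is one of the arguments for the telephone arm. A reader of the final report would take the percentage as an observed result.

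**Working it through.** The documents state no reach figure, so there is none to reproduce.

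**Inputs**
- Patients with diabetes (Table 1): Charlestown 1,085, Chelsea 2,691, Revere 2,120.
- Approximate recruitment targets (Table 1): 45, 85 and 85, which sum to 215.
- Planned enrollment (Section VI.d): 210, or 70 per arm; the two lifestyle arms hold 2 × 70 = 140.
- Assumed eligibility (Section V, Reach): 20%.

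**Formula.** Reach = participants / (eligibility rate × patients with diabetes). This reads the word population as patients with diabetes at the three centers.

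**Level under the plan's rule**
- 1,085 + 2,691 + 2,120 = 5,896, and 0.20 × 5,896 = 1,179.2.
- All participants: 210 / 1,179.2 = 17.8%.
- Lifestyle arms only: 140 / 1,179.2 = 11.9%.
- For reference, against all patients with diabetes: 210 / 5,896 = 3.6%, and 140 / 5,896 = 2.4%.

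**Sensitivity to the eligibility rate** (rates other than 20% are assumed)

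| Eligibility | Denominator | 210 participants | 140 participants |
|---|---|---|---|
| 10% | 589.6 | 35.6% | 23.7% |
| 15% | 884.4 | 23.7% | 15.8% |
| 20% (plan) | 1,179.2 | 17.8% | 11.9% |
| 30% | 1,768.8 | 11.9% | 7.9% |

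The plan calls its 20% an upper limit. If that is right, 17.8% is the lowest value that full enrollment of center patients could give. The 30% row matters only if the unsourced limit is wrong.

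**Comparisons between centers.** At the Table 1 targets:
- Charlestown: 45 / 217.0 = 20.7%
- Chelsea: 85 / 538.2 = 15.8%
- Revere: 85 / 424.0 = 20.0%

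A common rate cancels in ratios. Charlestown to Chelsea is (45 / 1,085) / (85 / 2,691) = 1.31 at any shared rate. It changes only if the rates differ. With 20% at Charlestown and 15% at Chelsea (assumed), Chelsea becomes 85 / 403.65 = 21.1%, and the order of the two reverses.

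**Outside recruits.** With the 20% kept and a share s of the 210 from outside removed, reach = 210 × (1 − s) / 1,179.2. The documents give no value for s. Assumed shares of 10%, 20%, 30% and 50% give 16.0%, 14.2%, 12.5% and 8.9%.

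**Another reading of the population.** If it meant everyone served by the centers, the Table 1 prevalences imply 1,085 / 0.10 + 2,691 / 0.19 + 2,120 / 0.15 = 39,146 people. Then 20% is 7,829, and reach is 210 / 7,829 = 2.7%. The sentence before the 20% in the Reach section speaks of patients with diabetes, which favors the reading used above, but the plan should say so.

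**The case against.** The strongest reply has four parts.

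**The measure is descriptive.** Section VI.d calls Aim 2 largely qualitative and says the study is not powered for RE-AIM measures. That stands, and it limits the weight of the point. A descriptive proportion still needs a denominator that was observed.

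**The trial may not have the count that would replace the 20%.** A reader might infer that the trial itself counts its eligible patients. The documents do not support this. They describe checks on individual patients, but they do not say that the whole registry is reviewed or that tallies are kept. Contact also depends on the provider's permission and on whether the patient is already interested in a concurrent study. Chart review cannot establish willingness or completion of the diary. What the trial can yield is a set of counts by stage.

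**Any fixed-size trial has a capped numerator.** This stands too. Observed denominators do not remove the cap, and enrolled over screen-eligible is a recruitment yield that depends on how many people were approached.

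**Reporting by center and by racial/ethnic group is already planned.** It is, but without a definition of the rate. A reader might also infer that differences between these groups would merely reflect recruitment quotas. Table 1 gives approximate targets by center only. The trial has no racial/ethnic quotas; the demographic targets in Section V belong to the preliminary interviews. As shown above, a common 20% cancels in such ratios.

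**Conclusion.** The concern holds for the level of reach. Under the stated rule, full enrollment yields 17.8% for all 210 participants or 11.9% for the 140 in the lifestyle arms, whatever the true number eligible. For the 210, true eligibility of 10% or 30% would give 35.6% or 11.9%. These figures rest on three assumptions: the population is patients with diabetes at the three centers, enrollment is complete, and all participants come from those centers.

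Ratios between centers or racial/ethnic groups are affected only if eligibility differs between them or outside recruits fall unevenly.

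A reader might infer that outside recruits will be counted toward reach. The plan does not say that they will, nor that they will not. This is an omission to close, and its size cannot be known from the documents.

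The consequence is confined to one descriptive Aim 2 measure. The weight-loss analysis and the cost analysis do not use it.

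**What to change.** Amend the Reach paragraph in Section V as follows.

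- **Retain tallies** by center and racial/ethnic group from the chart review, the letters and the screening.
- **Define the numerator** as participants with a primary care provider at the center in question. State whether it is all randomized participants or the two lifestyle arms only.
- **Report reach against staged denominators:** all patients with diabetes; chart-eligible among those reviewed; invited; screen-eligible among those screened.
- **Report recruits from outside the three centers separately.**
- **Keep the 20% version as a sensitivity figure only**, with its source and the meaning of population stated.

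The cost is wording plus the retention of screening tallies; no participant procedure is added. The reported percentage may move in either direction. Because enrollment is capped, the staged ratios describe recruitment yield and should be labeled that way.
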